4.5 Dose-Limiting Toxicity

A DLT is defined by the occurrence of any of the following toxicities possibly, probably or definitely related to BBI608 or BBI608 in combination with TMZ during the first 28 days of combination treatment:

- CTCAE Grade 3 thrombocytopenia with clinically significant bleeding
- CTCAE Grade 4 hematological toxicity.
- CTCAE Grade 3 non-hematological toxicity, except:
 - Grade 3 nausea, vomiting, anorexia, diarrhea or fatigue that persist < 7 days with appropriate supportive care.
- CTCAE Grade 4 non-hematological toxicity
 - Because DVT and PE are common complications among GBM patients, the first occurrence of DVT or PE will not be considered a DLT.
- Toxicities leading to delay of study treatment for ≥ 14 days
- During the post-surgical period and prior to initiation of combination therapy with BBI608 and TMZ, any grade 3 or greater hematological or non-hematological toxicity that cannot be attributed to the surgical procedure or to typical post-operative complications
- Any other toxicity that in the view of the Principal Investigator represents a clinically significant hazard to the patient

Whether a DLT has occurred will be assessed during the 28 days of the first cycle of combination treatment with TMZ and during the run in and post-operative period of Arm A. DLT will be determined from adverse events and changes from baseline in physical examination findings and in laboratory parameters.

To be considered evaluable for DLT, compliance with the assigned dose of BBI608 and TMZ must be $\geq 80\%$. Patients who do not complete 28 days of combination therapy for reasons other than DLT or patients who are not eligible for DLT assessment may be replaced. Adverse events considered related to TMZ only will not be considered DLTs for BBI608 in combination with TMZ.

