7.3 Treatment Compliance

A patient is considered compliant with the study protocol when he or she takes at least 80% of both the assigned study medication and TMZ. Treatment compliance will be monitored via Patient Diary in order to verify the Per Protocol patient population.

BBI608 and TMZ compliance will be calculated using the following equation:

$$\% \text{ Compliance} = \frac{\text{Number of capsules actually ingested in a given time period}}{\text{Number of capsules that should have been ingested per dose level}} \times 100$$

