4.2. Statistical decision rules

4.2.1. Phase Ib

4.2.1.1. Dose escalation and de-escalation

Dosing of BBI608 in each arm of this trial will be initiated at 480 mg twice daily; this dose is the monotherapy RP2D for BBI608 and is also the RP2D of BBI608 in combination with weekly paclitaxel or capecitabine. The BBI608 dose can be modified according to the following schedule:

Dosing Level	Description
Initial Dose	480 mg twice daily (960 mg total daily)
Modification Level –1	240 mg twice daily (480 mg total daily)
Modification Level—2	80 mg twice daily (160 mg total daily)
Modification Level—3	80 mg once daily (80 mg total daily)

The dose of TMZ can be escalated from 150 mg/m² daily to 200 mg/m² daily as per standard TMZ dosing guidelines for patients who complete at least one cycle at 150 mg/m².

Number of Subjects with DLT at a Given Dose Level for a Given Study Arm	Dose De-escalation Decision Rule
≤ 1 out of 6	This dose level will be considered RP2D for the combination regimen (BBI608+TMZ)
≥ 2 out of 6	Initial dose level will be reduced to a dose chosen by the Investigator and BBI medical monitor. Six (6) additional subjects will be entered at this lower dose level and evaluated for DLT over the first 28 days of combination therapy.

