Relative dose [RD]: The basic intent is to evaluate dose per *week* factoring in dose reductions or interruptions.

- Relative dose by period (Arm A subjects), by cycle and overall
 - By period RD (%) = $100 \times [\text{cumulative dose in the period}] / [\text{intended cumulative dose per period}]$
 - By cycle RD (%) = $100 \times [\text{cumulative dose in the cycle}] / [\text{intended cumulative dose per cycle}]$
 - Overall RD (%) = $100 \times [\text{overall cumulative dose}] / [\text{total planned or intended dose}]$
- For a combination regimen
 - if a study drug is discontinued prematurely while other study drug(s) are continued, then the RD is 0 for the discontinued study drug until all other study drug(s) of the regimen are discontinued

Relative Dose Intensity (RDI): The basic intent is to evaluate dose per *week* factoring in dose reductions, interruptions, or delays.

- Relative dose intensity (RDI) by period (Arm A subjects), by cycle and overall
 - Intended DI (*dose unit/week*) = [intended cumulative dose per period/cycle] / [intended number of *weeks* in a period/cycle]
 - By period RDI (%) = $100 \times [\text{by period actual DI}] / [\text{intended DI}]$
 - By cycle RDI (%) = $100 \times [\text{by cycle actual DI}] / [\text{intended DI}]$
 - Overall RDI (%) = $100 \times [\text{overall actual DI}] / [\text{intended DI}]$

Note:

- The intended dose level is fixed at the start of treatment rather than the start of a cycle.

- The intended cumulative dose of BBI608 per period (for Arm A subjects) is calculated by (intended dose level per day) x (intended period duration in days).
- The intended cumulative dose of BBI608 per cycle is calculated by (intended dose level per day) x (intended cycle duration in days).
- Dose unit of BBI608 is mg; dose unit of TMZ is mg/m².

Treatment compliance

BBI-608 compliance will be summarized by period (for Arm A), for cycle 1 (Arm A post-operative and Arm B patients) and overall

1. By Period (Arm A): Treatment compliance for BBI-608 is defined as below, (Cumulative actual total dose per period/ total planned or intended dose per period) x 100=% compliance
2. By Cycle (Arm A post-operative and Arm B): Treatment compliance for BBI608 is defined as below, (Cumulative actual total dose per cycle /total planned or intended dose per cycle) x 100= % compliance
3. Overall: Treatment compliance for BBI-608 is defined as below, (Cumulative actual total dose /total planned or intended dose) x 100= % compliance

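### SAP 8.2.1 computes BBI608 compliance as relative dose against the starting dose, so a fully adherent patient with a directed reduction, hold or early stop is reported below 100%, unlike under protocol 7.3

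*SAP*

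**What the plan says.** **Protocol.** Section 7.3 gives one compliance formula for both drugs: capsules taken in a period, divided by "Number of capsules that should have been ingested per dose level". A patient is compliant when he or she "takes at least 80% of both the assigned study medication and TMZ". The stated use is: "Treatment compliance will be monitored via Patient Diary in order to verify the Per Protocol patient population". Section 4.5 has a parallel rule for DLT evaluability, under which "compliance with the assigned dose of BBI608 and TMZ must be" at least 80%. Section 7.2.1 directs a step down to the next modification level for persistent intolerable Grade 2 symptoms and for Grade 3 or 4 symptoms. It allows or recommends a short interruption beforehand.

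**SAP 8.2.1.** BBI608 compliance is reported by period (Arm A), for Cycle 1, and overall. The cycle version is "Cumulative actual total dose per cycle /total planned or intended dose per cycle) x 100= % compliance"; the period and overall versions have the same form. The notes just above that heading state "The intended dose level is fixed at the start of treatment rather than the start of a cycle" and "The intended cumulative dose of BBI608 per cycle is calculated by (intended dose level per day) x (intended cycle duration in days". A BBI608 cycle counts for at least 28 days, and the intended end of treatment is the last day of the last cycle started. Relative dose is defined by the same ratio, and the SAP says its purpose is to take account of reductions and interruptions.

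**TMZ.** SAP compliance counts treatments given against treatments due. SAP 4.2.1.1 adds: "The dose of TMZ can be escalated from 150 mg/m² daily to 200 mg/m² daily", for patients who complete at least one cycle at the lower dose.

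**The concern.** The two documents give different denominators for a quantity with the same name, and the SAP gives no reason for the change. Relative dose asks how much of the starting plan was delivered. Compliance asks whether the patient took what was prescribed. With the starting dose as denominator for both, the BBI608 compliance line repeats relative dose, and a reduction made for toxicity reads as missed capsules.

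Cycle 1 is the only single cycle for which the SAP tabulates compliance. It is also the DLT window, and the protocol's Per Protocol definition rests on 80% of one cycle. A reader of the report could easily take the Cycle 1 figure as the one those rules refer to.

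**Working it through.** Neither document gives a worked compliance figure, so there is nothing to reproduce.

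**Inputs**
- Starting dose 960 mg/day; first modification level 480 mg/day (SAP 4.2.1.1).
- Cycle of 28 days; intended duration to the end of the last cycle started (SAP 8.2.1).
- Capsules of 80 mg (protocol 7.1), so 12 per day at 960 mg and 6 per day at 480 mg.
- The patient takes every capsule prescribed.

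**Formulas**
- SAP, Cycle 1: 100 × mg taken / (960 × 28) = 100 × mg taken / 26,880.
- Protocol: 100 × capsules taken / capsules due at the dose level.

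**Reduction to 480 mg/day in Cycle 1**
- After day 10: SAP (10 × 960 + 18 × 480) / 26,880 = 18,240 / 26,880 = 67.9%. Protocol: (120 + 108) / (120 + 108) = 228 / 228 = 100%.
- After day 14: SAP (14 × 960 + 14 × 480) / 26,880 = 20,160 / 26,880 = 75.0%. Protocol: 100%.
- Three-day hold after day 7, then 480 mg/day: SAP (7 × 960 + 18 × 480) / 26,880 = 15,360 / 26,880 = 57.1%. Protocol: 100% if no capsule is due on a directed hold day, which section 7.3 does not state.

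**Early stop at full dose (Arm B, last dose on day 4 of cycle 3)**
- Days dosed: 28 + 28 + 4 = 60. Intended days: 3 × 28 = 84. SAP overall compliance: 60 / 84 = 71.4%. Protocol: 100% if capsules are due only up to the last prescribed dose.

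**If the SAP ratio were used for an 80% cut**
- With d full-dose days followed by 480 mg/day, the ratio is (d + (28 − d)/2) / 28. It reaches 80% when d ≥ 16.8, so at least 17 full-dose days would be needed (17 days gives 80.4%, 16 days gives 78.6%).

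**TMZ relative dose, if the fixed-level note is applied at 150 mg/m²**
- One cycle at 150 and five at 200, with five dosing days per cycle cancelling: (150 + 5 × 200) / (6 × 150) = 1,150 / 900 = 127.8%.

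**The case against.** **The link is inferred.** The fixed-level note sits with relative dose and relative dose intensity, ahead of the compliance heading, and nothing cross-refers. That is true. But it is the SAP's only definition of the intended level, and overall compliance and overall relative dose share the same denominator wording. A programmer would have no other rule to apply.

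**Protocol 7.3 does not say current dose level.** Section 7.1.2 speaks of the level at which a patient is enrolled, which could mean the starting dose. Against that, 7.2.1 uses dose level for the modification steps, and 7.3 speaks of assigned medication. The current-level reading fits better, but it is a reading.

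**Adherence is visible elsewhere.** The SAP also reports the percentage of days with at least 960 mg, at least 480 mg and any dose, plus a drug accountability listing. So it would be wrong to infer that the SAP output says nothing about adherence. The daily summaries help only in part. The patient reduced after day 10 scores 10/28 = 35.7%, 100% and 100%. A patient never reduced, who from day 11 skips one of the two daily doses, scores the same on all three and also shows 67.9% on the SAP ratio. Only the protocol formula separates them: 228/228 = 100% against 228/336 = 67.9%.

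**A reader might infer that the formula changes who is analysed.** The documents do not support that. SAP items 1 to 3 carry no threshold; the bands with an 80% boundary apply to the daily measure. SAP section 6 has no Per Protocol set. For DLT, SAP 3.1.1 refers back to protocol 4.5, and under protocol 4.4 a patient with a DLT is evaluable in any case.

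**A reader might infer that TMZ relative dose hides missed cycles.** The treatment count shows them: one of six cycles missed gives 25/30 = 83.3%. The SAP writes out no intended cumulative TMZ dose, the increase is conditional, and the SAP says only that exposure may be summarised as relative dose.

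**Conclusion.** The point holds as a mismatch of definitions in a descriptive table. As written, SAP BBI608 compliance duplicates relative dose. It reports fully adherent patients at 67.9% or 75% in Cycle 1 after a reduction on the days shown, and at 71.4% overall after an early stop, where the protocol formula gives 100%.

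This rests on three assumptions: that the fixed-level note governs the compliance denominator, that protocol 7.3 refers to the level assigned at the time, and that capsules are due only up to the last prescribed dose. A cohort that starts at a lower level has that level as its denominator, so its starting dose alone does not lower the ratio.

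No SAP endpoint or analysis set changes. The protocol's 80% rules for the Per Protocol set and DLT evaluability would be affected only if the SAP ratio were used to apply them. A starting-dose denominator is appropriate for relative dose and relative dose intensity; the fault is in using it for compliance. For TMZ, the only point is that the relative-dose denominator is unstated: applied at 150 mg/m², it gives more than 100% in patients who escalate.

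**What to change.** In SAP 8.2.1, items 1 to 3:

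- Compute BBI608 compliance as in protocol 7.3. The denominator is the dose due at the level assigned on each day, up to the last prescribed dose.
- State how directed hold days are counted, since protocol 7.3 leaves this open.
- If the assigned daily dose is not recorded during re-escalation, use the assigned modification level.
- Restrict the fixed starting-dose note to relative dose and relative dose intensity.
- State the TMZ denominator wherever TMZ relative dose is reported.

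The cost is SAP wording and programming, using dosing records and the patient diaries that protocol 7.3 already requires. Whether those sources hold the assigned dose for every day should be checked first; the documents do not say, which is why the fallback is needed. No dose or treatment rule changes.

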8.2.2. Analysis for Primary Endpoint

8.2.2.1. DLT (Phase 1b)

Dose Limiting Toxicity (DLT) is the primary endpoint of the dose escalation component of the study. Listings of the DLTs will be provided for Arm A (BBI608 plus TMZ) and Arm B (BBI608 plus TMZ).

8.2.2.2. Progression Free Survival at 6 months (PFS-6, Phase 1 and Phase 2)

PFS data will be analyzed by arm. PFS summary in Arm B will be provided only when the number of patients in that arm is at least 10. The same rule applies to Arm A data.

Progression free survival at 6 months (PFS-6) is defined as the proportion of patients who have survived without objective disease progression per RANO criteria for at least 6 months after enrollment. The censoring rules for PFS will be detailed in 10.2. If a patient has not progressed or died at the time of analysis, PFS will be censored on the date of the last tumor assessment. This includes patients who are lost to follow-up or have withdrawn consent.

PFS in months is calculated as (first event date/censored date – date of first dose of any study drug + 1)/30.4375. Estimates of the PFS curves at 6 months will be obtained using the Kaplan-Meier method and will be presented along with the 80% CI using the normal approximation to the log transformed cumulative hazard rate.

8.2.3. Analyses for Secondary Endpoints

8.2.3.1. Other Efficacy Endpoints Analysis

Response data (including Disease Control Rate (DCR) and Objective Response Rate (ORR)), progression free survival (PFS) and overall survival (OS) data will be analyzed by arm. Response data summary for Arm B will be provided only when the number of patients in that arm is at least 5. The same rule applies to Arm A data. Otherwise, only response data listing will be provided.

Summary for survival data (including PFS and OS) will follow the rule of ‘at least 10’ as described in Section 8.2.2.2.

DCR is defined as the proportion of patients with a documented complete response, partial response, and stable disease (CR + PR + SD) based on RANO. The primary estimate of DCR will be based on the FAS population. DCR will be summarized for each treatment arm along with the corresponding exact 2-sided 95% CI using the Clopper Pearson method.

ORR is defined as the proportion of patients with a documented complete response and partial response (CR + PR) based on RANO. The primary estimate for ORR will be based on the FAS population.

ORR will be analyzed similarly as DCR. Best Overall Response (BOR) will also be summarized in a similar fashion.

PFS in the full analysis set is defined as the time from exposure to any study drug to the first objective documentation of disease progression or death due to any cause. If a patient has not progressed or died at the time of analysis, PFS will be censored on the date of the last tumor assessment. PFS is calculated as described in section 8.2.2.2.

PFS will be reported as the median event time (and other quartiles) and the corresponding 2-sided 95% CI for each treatment arm. Estimates of the PFS curves obtained from the Kaplan-Meier method will be presented along with a graphical presentation of PFS curves.

OS is defined as the time from exposure to any study drug to death from any cause. Patients who are alive at the time of analysis or who have dropped out will be censored at their last date known to be alive. OS in months is calculated as $(\text{date of death/Last known to be alive date} - \text{date of first dose of any study drug} + 1)/30.4375$.

The survival experience of patients will be summarized by the Kaplan-Meier method.

8.2.3.2. PK Analysis

Nuventra Pharma Sciences will compute PK parameters by noncompartmental analysis using Phoenix WinNonlin version 6.3 (Certara, L.P., Princeton, NJ), and generate TLFs using a validated version of R version 3.4.0 or later (R Foundation for Statistical Computing, Vienna, Austria).

Demographics for patients included in the PK Analysis Set will be summarized in the PK report, summarized by Arm.

8.2.3.2.1. PK Concentrations

Plasma concentrations will be listed and summarized by BBI608 dose, concomitant treatment, Arm, day, and nominal timepoint using descriptive statistics, including N, mean, standard deviation (SD), coefficient of variation (CV), minimum, maximum, and median. Imputation of concentration data BLQ is described in Section 7.5.

Actual elapsed time from dosing and the difference between actual and nominal time will be included in individual subject listings. Individual subject plasma concentrations versus actual elapsed time will be presented on spaghetti plots on linear scale and semi logarithmic scale. Mean plasma concentrations versus nominal time will be plotted on both linear and semi-logarithmic scales by day, BBI608 dose, concomitant therapy and Arm, as appropriate.

8.2.3.2.2. Pharmacokinetic parameters

Following pharmacokinetic parameters will be calculated for Cycle 1 Day 1 and Cycle 1 Day 5 as data allow:

- The maximum plasma concentration (C_{max})
- The time to reach maximum plasma concentration (T_{max})
- The area under the plasma concentration-time curve from zero to infinity (AUC_{inf}) [Cycle 1, Day 1 only]
- The percentage of the AUC extrapolated beyond the last measurable concentration (AUC_{ext})
- The AUC from time zero to time of the last measured concentration above the limit of quantification (AUC_{last})
- Time of last measurable (positive) observed concentration (T_{last})
- The AUC during a dosing interval at steady state (AUC_{tau}) [Cycle 1, Day 5 only]
- The elimination rate constant (λ_z)
- Upper limit on time for values to be included in the calculation of λ_z (λ_z _upper)
- Lower limit on time for values to be included in the calculation of λ_z (λ_z _lower)
- Number of points used in computing λ_z (λ_z _No)
- Apparent systemic clearance (CL/F)
- Apparent total volume of distribution in the terminal phase (V_z/F)
- Terminal phase half-life (t_{1/2})

Additionally for Cycle 1 Day 5, parameters listed below will be calculated where possible:

- Minimum concentration at steady state (C_{min,ss})
- Total body clearance at steady state (CL_{ss}/F)
- The accumulation ratio for C_{max} and AUC_{tau} will also be calculated (R_{acc} C_{max} and R_{acc} AUC_{tau}).

Derived plasma PK parameters will be summarized by day, BBI608 dose, concomitant treatment and Arm, as appropriate, using descriptive statistics including N, mean, SD, CV, geometric mean, geometric CV, minimum, maximum, and median. For T_{max} and T_{last}, N, minimum, maximum, and median will be reported.

All PK parameters will be estimated using actual elapsed time from dosing.

8.2.3.3. PD/Biomarker Analysis

BBI is exploring several biomarkers in tumor tissues. Tumor archival tissue and biopsies will be collected as described in the Laboratory Manual. The correlations between the biomarker results, pharmacokinetic parameters, and measures of anti-tumor/anti-cancer efficacy signals or safety signals will be explored if data allows and it is deemed appropriate.

8.2.4. Analysis for Other Safety Endpoints

All adverse events, lab, vital signs, physical exam, and ECG data analyses will be summarized based on the full analysis set. These data will be summarized by arm.

8.2.4.1. Adverse Events

Overall Summary of AEs

An AE will be regarded as **treatment-emergent**, if

- it occurs for the first time on or after the first dose date of either BBI 608 or TMZ up to 30 days after the last dose of study treatment; or
- it occurs prior to first dose date of either BBI 608 or TMZ and worsens in severity on therapy or up to 30 days after the last dose of study treatment

Last dose of study treatment will be obtained from either drug administration or end of treatment CRF, whichever comes later.

Concurrent conditions from CRF collecting Adverse Event include any event or condition that was active at the time of starting on study. Entries have a start date and a severity grade. This will be considered a baseline AE and be used to derive treatment-emergent AE.

Adverse events will be coded by SOC and PT using the MedDRA[®] version 19.0. The severity of AEs will be graded by the investigator using NCI CTCAE Version 4.0. The verbatim term will be included in the AE listings.

An overview of treatment-emergent adverse events (TEAEs) will be provided. The number and percentage of subjects with following will be summarized for:

1. Subjects with at least one TEAE
2. Subjects with TEAE of CTCAE grade 3 or higher
3. Subjects with serious TEAE
4. Subjects with serious TEAE related to BBI608
5. Subjects with serious TEAE related to TMZ
6. Subjects with BBI 608 related TEAE
7. Subjects with BBI 608 related TEAE of CTCAE grade 3 or higher
8. Subjects with TMZ related TEAE
9. Subjects with TMZ related TEAE of CTCAE grade 3 or higher
10. Subjects with TEAE related to study drug (BBI608 or TMZ)
11. Subjects with study drug (BBI608 or TMZ) related TEAE of CTCAE grade 3 or higher
12. Subjects with TEAEs leading to BBI-608 being held
13. Subjects with TEAE leading to dose reduction BBI-608
14. Subjects with TEAE leading to BBI-608 dose discontinuation
15. Subjects with TEAE leading to TMZ being held
16. Subjects with TEAE leading to dose reduction of TMZ

Summary of AEs by System Organ Class and Preferred Term

The number and percentage of subjects with TEAEs by SOC and PT and maximum CTCAE grade will be summarized. A summary of TEAEs of CTCAE grade 3 or higher (Grade 3, 4, 5) will be presented by SOC and PT and maximum CTCAE grade. A summary of TEAEs by SOC, PT and maximum grade will be presented in the descending order of frequency counts for all grades. The most commonly reported AEs using different cutoffs (e.g., 2%, 5% or 10% or more of patients in either arm) may also be summarized by PT as needed for various reporting purposes. Adverse events associated with dose held/dose reduction of either BBI608 and/or Temozolomide will also be summarized by SOC and PT and maximum CTCAE grade.

Treatment Related TEAE

AEs reported with a relationship to a treatment considered by the investigator to be 'possible', 'probable' or 'definite' will be considered "Related" to study treatment or combination drug, respectively. AEs reported with a relationship to a treatment considered by the investigator to be "unlikely" or "unrelated" will be considered as "Not Related" to study treatment or TMZ, respectively. Missing relationship will be considered as "Related". Similar summaries of all causality AEs will be provided along with TEAEs leading to dose modification, reduction, or discontinuation.

Serious AE and Death

Treatment emergent SAEs and treatment related SAEs will be summarized by MedDRA SOC and PT and Maximum CTCAE grade.

Patients who experienced a SAE during AE reporting period will be listed for all safety patients. The number and percentage of patients who experience any treatment emergent SAE will be summarized by SOC, PT and maximum CTCAE grade. Similar summary for treatment related TESAE will be provided as well.

Deaths that occur on or after the first dose of study treatment and within 30 days of last dose of any study treatment will be summarized. The number and percentage of subjects who died during the study treatment and within 30 days after the last dose will be presented.

TEAE or TESAEs leading to death will also be summarized by MedDRA, SOC, PT, and Maximum CTCAE grade.

A listing of death data will also be provided and it will include all deaths that occurred during the reporting period for deaths, which starts from the signing of informed consent to the end of the follow up period. The listing will include date of death, and the number of days relative to the administration of first and last dose.

Adverse Events of Clinical Relevance

Selected adverse events are specified for additional focus due to the potential clinical significance of the event and/or the potential association with the investigational product. These events include those in the standard MedDRA query (SMQ) terms (narrow or broad, as noted):

Table 1. Adverse Events of Clinical Relevance SMQ terms

MedDRA v20.0 Term	SMQ class
Myocardial infarction	Broad
Supraventricular tachycardia	Narrow
Non-infectious diarrhea	Broad
Gastrointestinal haemorrhage	Narrow
Gastrointestinal obstruction	Narrow
Acute kidney injury	Narrow (acute renal failure)

Tables listing the incidence and maximum severity of these events in the safety population will be generated.

